9.6 Pharmacodynamics

Refer to Section 9.8.

9.7 Pharmacogenomics

Refer to Section 9.8.

9.8 Biomarkers

A variety of factors that could potentially predict clinical response and incidence of AEs to nivolumab + ipilimumab combined therapy and/or nivolumab monotherapy will be investigated in peripheral blood and in tumor specimens taken from all participants prior to treatment and as outlined in the protocol. Data from these investigations will be evaluated for associations with efficacy endpoints. In addition, these analyses will provide the necessary data to identify and validate biomarkers with predictive versus prognostic value. The biomarker-sampling schedule for this study is provided in Table 9.8-1. A separate manual outlining details of biomarker sample collection and handling will be provided to participating sites.

Table 9.8-1: Biomarker Sampling Schedule for Nivolumab, Ipilimumab, and Placebo for All Study Parts and Arms

Study Day (1 Cycle = 2 Weeks)	Event (Relative to Dosing) Hour	^a Tumor Biopsy	Whole Blood DNA	Peripheral Blood RNA ^b	MDS C	Serum ^b	ctDNA ^c	Anti- SARS- CoV-2 serology ^d
Screening		X						
C1D1	Predose		X	X	X	X	X	X
C2D1	Predose						X	
C4D1	Predose					X		
C5D1	Predose						X	
C7D1	Predose				X	X		
C9D1	Predose						X	
C12D1	Predose							X
Follow-up Visit 2								X

AE, adverse event; ctDNA, circulating tumor DNA; C, cycle; D, day; MDSC, myeloid-derived suppressor cells; SAE, serious adverse event; SARS-CoV-2, severe acute respiratory syndrome coronavirus 2

^a Baseline tumor samples are mandatory and an optional tumor sample will be collected upon recurrence.

^b Sample collection upon > Grade 3 non-laboratory drug-related AE and/or laboratory abnormalities regarded as a drug-related SAE, to be collected when clinically safe and feasible.

^c Subsequent ctDNA sample collections will be aligned with tumor assessments performed on Weeks 23, 36, and 52 (+/- 1 week window). If a tumor assessment is not performed, ctDNA sampling is not required.

^d A sample is also collected approximately 4 weeks after a suspected or confirmed SARS-CoV-2 infection to be used for potential future measurements of anti-SARS-CoV-2 serology (anti-SARS-CoV-2 total or immunoglobulin G (IgG))

9.8.1 Additional Research Collection

This protocol will include residual sample storage for additional research (AR).

For All US sites:

Additional research is mandatory for all investigational sites in the US.

For non-US Sites

Additional research is optional for all study participants, except where retention and/or collection is prohibited by local laws or regulations, ethics committees, or institutional requirements.

This collection for additional research is intended to expand the translational R&D capability at Bristol-Myers Squibb, and will support as yet undefined research aims that will advance our understanding of disease and options for treatment. It may also be used [REDACTED] [REDACTED] for analysis, and advancement of pharmacodiagnostic development to better target drugs to the right patients. This may also include genetic/genomic exploration aimed at exploring disease pathways, progression and response to treatment etc.

Sample Collection and Storage

All requests for access to samples or data for additional research will be vetted through a diverse committee of the study sponsor's senior leaders in Research and Development (or designee) to ensure the research supports appropriate and well-defined scientific research activities.

- Residual DNA from whole blood, serum, circulating tumor DNA (ctDNA), peripheral blood RNA, and DNA and RNA from tumor biopsy tissue, (see [Table 9.8.1-1](#)) will also be retained for additional research purposes

Samples kept for future research will be stored at [REDACTED] an independent, BMS-approved storage vendor.

The manager of these samples will ensure they are properly used throughout their usable life and will destroy the samples at the end of the scheduled storage period, no longer than fifteen (15) years after the end of the study or the maximum allowed by applicable law.

Transfers of samples by research sponsor to third parties will be subject to the recipient's agreement to establish similar storage procedures.

Samples will be stored in a coded fashion, and no researcher will have access to the key. The key is securely held by the Investigator at the clinical site, so there is no direct ability for a researcher to connect a sample to a specific individual.

Further details of sample collection and processing will be provided to the site in the procedure manual.

A variety of factors that could potentially predict clinical response and incidence of AEs to nivolumab and ipilimumab will be investigated in peripheral blood and in tumor specimens taken

from all participants prior to randomization. Data from these investigations will be evaluated for associations with DFS, OS, and distant metastasis-free survival and/or safety (adverse event) data. In addition, analyses of markers between the 2 treatment arms will provide the necessary data to identify and validate biomarkers with predictive vs prognostic value. All samples collected may also be used for future exploratory analyses (unless restricted by local requirements and/or institutional policies) to assess biomarkers associated with RCC or immunotherapy treatment. Complete instructions on the collection, processing, handling and shipment of all samples described herein will be provided in a separate procedure manual.

Table 9.8.1-1: Residual Sample Retention for Additional Research Schedule

Sample Type	Timepoints for which residual samples will be retained
Whole blood (DNA)	All
Serum	All
ctDNA	All
Peripheral Blood RNA	All
Tumor Biopsy (DNA and RNA)	Screening and recurrence

9.8.2 Tissue Specimens

Sufficient tumor tissue specimens collected within 3 months prior to enrollment, preferably at the time of nephrectomy, will be required in the form of a FFPE tissue block or 20 unstained slides. A minimum of 10 slides will be acceptable if tumor tissue is limited. In these situations, it is recommended to consult with the protocol team to discuss the specifics of the case.

The tumor sample may be used to assess putative predictive biomarkers of nivolumab and ipilimumab efficacy and/or to better characterize the tumor-immune microenvironment. Various molecular markers with potential predictive value for the treatment of RCC with nivolumab, ipilimumab and other immunotherapies are currently under investigation and may be assessed in this study. These tumor tissue biomarkers include, but are not limited to PD-L1, PD-1, PD-L2, TILs or subpopulations of TILs, a Th1 immune mRNA expression signature. In addition, tumor samples will also be used for assessment of tumor recurrence score based on gene signature analysis.⁵⁴ These tumor samples may also be used to further characterize the tumor-immune microenvironment through assessment of markers that may be associated with the efficacy of nivolumab and ipilimumab, including but not limited to other T cell checkpoint receptors and ligands (eg, Lag-3, Tim-3), and intratumoral immune cell subsets, including macrophages, natural killer (NK) cells and B cells.

In addition, it is recommended, although optional, for tumor tissue samples to be collected upon recurrence. These samples may be used for the assessment of markers implicated in resistance to immunotherapeutic agents, including but not limited to other T-cell checkpoint receptors and

ligands (eg, Lag-3, Tim-3) and intratumoral immune cell subsets, including but not limited to, T-regulatory cells and myeloid derived suppressor cells. These samples may also be used to investigate the effect of nivolumab and ipilimumab on the expression of potentially relevant predictive and/or prognostic RCC biomarkers. Both the nephrectomy tumor sample and the sample collected upon recurrence may be retrospectively assessed for the expression of other immune-related genes, RNAs and/or proteins, or for the presence of immune cell populations using a variety of methodologies inclusive of, but not limited to IHC, qRT-PCR, genetic mutation detection and fluorescent in-situ hybridization (FISH).

9.8.3 Exploratory Serum Biomarkers

Blood samples for exploratory serum biomarker analyses will be drawn at the time points specified in [Table 2-2](#) and [Table 2-3](#). Additionally, serum samples will be collected when clinically safe and feasible, upon occurrence of a \geq Grade 3 drug-related AE and/or any lab abnormality regarded as a drug-related SAE, and upon recurrence. Blood samples will be collected and processed for serum and then put in frozen storage. Serum samples may be assessed by ELISA, seromics, microRNA profiling, ctDNA measurements, metabolomics and/or other relevant multiplex-based protein assay methods for immune or RCC-related factors that will predict for nivolumab or ipilimumab benefit or correlate with nivolumab or ipilimumab-related AEs. Numerous potential serum-based biomarkers are currently under investigation for their potential to predict or correlate with safety or efficacy to nivolumab, ipilimumab or other immunotherapies, including but not limited to levels of soluble PD-L1, anti-tumor antibodies, cytokines, chemokines, inflammatory factors, NKG2D ligands (eg, soluble MICA), ctDNA, and microRNAs (such as, but not limited to, miR-513 and miR19b).

9.8.4 Peripheral Blood RNA

Gene expression analyses of RNA derived from whole blood may provide information on the broad effects of nivolumab and ipilimumab on immune modulation. Thus, genomic expression patterns of whole blood collected at the time points in specified in [Table 2-2](#) and [Table 2-3](#) may be assessed by Affymetrix microarray profiling, qRT-PCR or other gene expression profiling technology, with a particular emphasis on genes with relevant immune function.

9.8.5 Myeloid-Derived Suppressor Cells

Myeloid-derived suppressor cells (MDSCs) are an immune cell population capable of suppressing T cell activation and proliferation. MDSCs will be measured at baseline and on-treatment as described in [Table 9.8-1](#) to assess pharmacodynamic changes or associations with outcome.

9.8.6 Peripheral Blood DNA Mutation Research

The presence of cell-free DNA in circulating peripheral blood is a well-documented phenomenon. Fragments of DNA are shed into the blood stream from proliferating cells or from cells undergoing apoptosis or other forms of cell death. In patients with cancer, a fraction of this DNA is tumor-derived and is termed ctDNA. Small fragments of DNA, averaging between 180 to 200 base-pairs and representing segments of specific genes, can be amplified with PCR and then sequenced. Moreover, several studies have detected mutations in ctDNA that exactly correspond to mutations

from the parent tumor, using tissue and plasma from participants with known driver mutations in melanoma or head and neck cancer. Beaming technology may be utilized to count the frequency of mutations in the circulation. Correlation analyses with tumor will be warranted where the data are available. ctDNA will be investigated as a prognostic and predictive biomarker and will be used to monitor changes in tumor mutations during treatment.

9.8.7 Whole Blood for Genotyping

Whole blood samples for exploratory pharmacogenetic assessment will be collected from all participants. Genomic DNA will be extracted and subsequently assessed for SNPs and other genetic variations in candidate genes that may predispose participants to nivolumab or ipilimumab benefit or AEs (unless restricted by local requirements.) Such genes include, but are not limited to, PD-1, PD-L1, PD-L2 and CTLA-4. Additional use of these data may include correlative analyses aimed at identifying genotypic associations with clinically relevant biomarkers identified by other methodologies described in this section. This sample may be assessed for whole exome sequencing (WES) and rearrangements in the TCR in T cells within the peripheral blood. WES is an efficient way to identify genetic variants that alter protein sequences. An assessment of somatic TCR rearrangements by PCR, sequencing or NextGen sequencing approach will provide information regarding the clonality of a T cell repertoire, which may change with nivolumab and/or ipilimumab treatment. In addition, baseline T cell repertoire may be predictive of nivolumab and/or ipilimumab benefit.

9.8.8 Immunogenicity Assessments

Blood samples for immunogenicity analysis will be collected. Samples collected from participants receiving nivolumab and/or ipilimumab will be evaluated for development of Anti-Drug Antibody (ADA) by a validated electrochemiluminescent (ECL) immunoassays.

Samples may also be analyzed for neutralizing antibodies and PK samples (please refer to [Table 9.5-1](#) for immunogenicity sampling schedule) may be used for ADA analysis in the event of insufficient volume, to complete immunogenicity assessment, or to follow up on suspected immunogenicity-related AEs.

Further details of sample collection, processing, and shipment will be provided in the laboratory procedures manual.

9.8.9 Other Assessments

Serum will be collected for potential future measurements of anti-SARS-CoV-2 antibodies by serology (anti-SARS-CoV-2 total or immunoglobulin G [IgG]) to explore potential association with safety, efficacy, and/or immune biomarkers.

9.9 Health Economics OR Medical Resource Utilization and Health Economics

Health Economics/Medical Resource Utilization and Health Economics parameters will not be evaluated in this study.

10 STATISTICAL CONSIDERATIONS

10.1 Sample Size Determination

The modification to the study design outlined in revprot03 adds a monotherapy arm (nivolumab) and roughly doubles the total sample size with the first approximately 800 randomized 1:1 participants (Part A) to nivolumab + ipilimumab and placebo and the approximately 800 randomized 1:1:2 participants (Part B) to nivolumab + ipilimumab, placebo and nivolumab. Part A participants will be mutually exclusive from Part B participants. The combination analysis in Part A is preserved comparing the nivolumab + ipilimumab arm to the placebo arm in the first approximately 800 nivolumab + ipilimumab and placebo randomized 1:1 participants. Part B is added for the purposes 1) to compare monotherapy nivolumab to placebo and 2) to estimate the contribution of components for the combination of nivolumab + ipilimumab and monotherapy nivolumab.

This section is organized as follows. First, sample size calculations for Part A are presented. Second, the sample size calculations for Part B are presented. The Part B monotherapy comparison is between the nivolumab (approximately 400 participants) and placebo (approximately 200 participants) arms. The additional approximately 200 participants randomized to the nivolumab + ipilimumab arm in Part B will be included in the combination OS analysis hierarchically if the DFS monotherapy test is successful (for more details, see [Section 10.3.4](#)). In addition, these nivolumab + ipilimumab Part B participants will be compared to the nivolumab participants to assess the contribution of components (CoC), i.e. to directly estimate the hazard ratio and variance for the contemporaneously randomized nivolumab + ipilimumab versus nivolumab arms.

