4 OBJECTIVES AND ENDPOINTS

Table 4-1: Objectives and Endpoints

Objectives	Endpoints

Primary
 
 Part A: To compare disease-free survival (DFS) per Blinded Independent Central Review (BICR) of nivolumab combined with ipilimumab versus placebo infusions in participants with localized RCC, with a predominantly clear cell histology who have undergone a nephrectomy. Part B: To compare disease-free survival (DFS) per Blinded Independent Central Review (BICR) of nivolumab versus placebo infusions in participants with localized renal cell carcinoma, with a predominantly clear cell histology who have undergone nephrectomy. 	
The primary endpoint is DFS. The primary endpoint of DFS will be programmatically determined based on the disease recurrence date provided by BICR. DFS is defined as the time from randomization to development of local disease recurrence (ie, recurrence of primary tumor in situ or occurrence of a secondary renal [RCC] primary cancer), distant metastasis, or death, whichever came first. See Table 10.3.1-1 for censoring rules.

Secondary
 
 Part A: To compare OS, including the 5-year OS rates, of nivolumab combined with ipilimumab versus placebo infusions in participants with localized RCC with a predominantly clear cell histology who have undergone a nephrectomy. Part B: To compare overall survival (OS), including the 5-year OS rates, of nivolumab versus placebo infusions in participants with localized renal cell 	
 OS, defined as the time between the date of randomization and the date of death. For participants without documentation of death, OS will be censored on the last date the participants was known to be alive.

Table 4-1: Objectives and Endpoints

Objectives	Endpoints

carcinoma with a predominantly clear cell histology who have undergone a nephrectomy.
 
 Part B: To evaluate differences in disease-free survival (DFS) per Blinded Independent Central Review (BICR) and overall survival (OS) of contemporaneously randomized nivolumab combined with ipilimumab participants versus nivolumab participants with localized renal cell carcinoma, with a predominantly clear cell histology, who have undergone a nephrectomy. 	
 DFS and OS in contemporaneously randomized combination and monotherapy participants.

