10.2 Populations for Analyses

For purposes of analysis, the following populations are defined:

Population	Description
All enrolled participants	
 All participants who signed an informed consent form and were registered into the IRT.
All enrolled Part A participants	
 All Part A participants who signed an informed consent form and were registered into the IRT.
All enrolled Part B participants	
 All Part B participants who signed an informed consent form and were registered into the IRT.
All treated participants	
 All participants who received at least 1 dose of study drug.
All treated Part A participants	
 All Part A participants who received at least 1 dose of study drug. This is the primary dataset for the Part A drug exposure and safety analysis.
All treated Part B participants	
 All Part B participants who received at least 1 dose of study drug. This is the primary dataset for the Part B drug exposure and safety analysis.
All randomized participants	
 All participants who were randomized to any treatment arm in the study. This population is considered the population for the combination overall survival analysis contingent on the primary DFS monotherapy analysis (for more details, see Section 10.3.4).
All randomized Part A participants	
 All Part A participants who were randomized to any treatment arm in the study. This population is considered for Part A as the primary efficacy analysis population. Analysis of demography, protocol deviations, baseline characteristics, efficacy analysis and outcome research analysis will be performed in this population.
All randomized Part B participants	
 All Part B participants who were randomized to any treatment arm in the study. This population is considered for Part B as the primary efficacy analysis population. Analysis of demography, protocol deviations, baseline characteristics, efficacy analysis and outcome research analysis will be performed in this population.
PK participants	
 All randomized participants with available serum time-concentration data.

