10.3.4 Interim Analyses and Hierarchical Testing

The Statistical Analysis Plan will further describe the planned interim analyses.

Part A Combination Analyses Timing

One formal DFS interim combination analysis will be conducted at the time when approximately 88% (204) of the total DFS events in the combination and placebo arms have occurred and the time when the total enrollment of both Part A and Part B is expected to be complete. This formal comparison of DFS will allow for early stopping for superiority. The stopping boundaries at the interim and final analyses will be derived based on the exact number of DFS events using Lan-DeMets alpha spending function with O'Brien-Fleming boundaries. Note that if Part B enrollment is still ongoing at the time of observing the required number of events for the interim analysis and target number of events needed for the final analysis is projected to occur in a shorter time interval (approximately within 4 months), then the interim analysis of DFS will not be performed and only one final analysis of DFS will be conducted after the completion of enrollment in Part A and Part B (statistical significance of only one final analysis of DFS is 0.05 [two-sided]).

If the DFS combination analysis is significant, the OS combination analysis will be tested hierarchically. Formal OS interim combination analyses will be conducted at the time when the interim or final DFS combination analysis is significant. This formal comparison of OS will allow for early stopping for superiority.

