The OS combination analyses occurring at the time when the DFS combination analysis is significant either after the Part A (approximately 800) participants randomized to the nivolumab + ipilimumab and placebo arms have a minimum of 20 or 26 months of follow-up, which are expected to occur at approximately 56 (62% of the total events) and 62 (70% of the total events) months from study initiation, respectively. These are at equivalent times when the DFS combination analyses of Part A are expected to occur. However, in the situation when the DFS combination analysis is significant at 56 months but OS is not significant at that time, the 62 month DFS analysis will not be necessary and so the second OS combination interim analysis will occur at 70 months (82% of the total events) rather than 62 months (70% of the total events). At the 56- and 62-month (or 70-month) OS combination analyses, approximately 178 and 201 (or 235) events are expected providing 41% and 53% (or 68%) power to detect overall interim OS HRs of 0.68 (P

< 0.009) and 0.70 ($P < 0.012$) (or 0.74, $P < 0.023$), respectively, at the pre-specified alpha level using the Lan DeMets alpha spending function.

The final OS combination analysis will take place after the Part A (approximately 800) participants randomized to the nivolumab + ipilimumab and placebo arms have a minimum of 48 months of follow-up, which is expected to occur approximately 84 months from the start of the study. At the time of the final OS combination analysis, approximately 287 events are expected ensuring 85% overall power to detect a final OS hazard ratio of 0.79 ($P < 0.045$).

Part B Monotherapy Analyses Timing

Similarly, 1 formal DFS interim monotherapy analysis will be conducted at the time when approximately 80% (122) of the total DFS events in the monotherapy and contemporaneous placebo arms have occurred. This formal comparison of DFS will allow for early stopping for superiority. The stopping boundaries at the interim and final analyses will be derived based on the exact number of DFS events using Lan-DeMets alpha spending function with O'Brien-Fleming boundaries. Note that if the target number of events for the interim analysis and final analysis are projected to occur in a shorter time interval (approximately within 6 months), then the interim analysis of DFS will not be performed and only one final analysis of DFS will be conducted (statistical significance of only one final analysis of DFS is 0.05 [two-sided]).

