
If the interim or final DFS monotherapy analysis is significant, the OS monotherapy analysis will be tested hierarchically. The final OS analysis will take place with approximately 182 events among all randomized Part B participants in nivolumab and placebo arms, which is expected to be at approximately 104 months from the start of the study, providing a minimum of 48 months of follow-up. Approximately 182 events are expected, ensuring 44% overall power to detect a HR of 0.73 ($P < 0.045$). Two formal OS interim monotherapy analyses will be conducted, which will allow for early stopping for superiority. The first and second interim analyses of OS are planned to occur with 102 events (56% of the targeted OS events) and 146 events (80% of the targeted OS events) among the randomized participants in nivolumab and placebo arms, which are expected to be at approximately 76 months and 90 months from the start of the study. Approximately 102 and 146 events are expected providing 8% and 27% power to detect overall interim OS HRs of 0.56 ($P < 0.006$) and 0.67 ($P < 0.023$), respectively, at the pre-specified alpha level using the Lan DeMets alpha spending function.

In addition to the formal planned interim analyses for DFS and OS, the DMC will have access to periodic unblinded interim reports of efficacy and safety to allow a risk/benefit assessment. Details will be included in the DMC charter.

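### Sections 10.1 and 10.2 bring Part B participants into the combination OS test, but Section 10.3.4 builds that test on Part A alone and has no pooling step

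*Combined protocol and SAP*

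**What the plan says.** Three operative sections describe the population for the confirmatory OS comparison of nivolumab + ipilimumab with placebo.

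- Section 10.1: the additional Part B combination participants "will be included in the combination OS analysis hierarchically if the DFS monotherapy test is successful".
- Section 10.2, for the population of everyone randomized to any arm: "This population is considered the population for the combination overall survival analysis contingent on the primary DFS monotherapy analysis".
- Section 10.3.4: "If the DFS combination analysis is significant, the OS combination analysis will be tested hierarchically". For the last look, "The final OS combination analysis will take place after the Part A (approximately 800) participants randomized to the nivolumab + ipilimumab" and placebo arms have at least 48 months of follow-up, at about month 84. There, "approximately 287 events are expected ensuring 85% overall power to detect a final OS hazard ratio of 0.79", with P < 0.045.

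Sections 10.1 and 10.2 both send the reader to 10.3.4 for details. In 10.3.4 the monotherapy DFS result has a different role: "If the interim or final DFS monotherapy analysis is significant, the OS monotherapy analysis will be tested hierarchically". Table 4-1 in Section 4 lists the combination comparison with placebo only under Part A: "Part A: To compare OS, including the 5-year OS rates, of nivolumab combined with ipilimumab versus placebo infusions". Section 10.3.4 also defers detail to another document: "The Statistical Analysis Plan will further describe the planned interim analyses".

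**The concern.** Combination OS is a formal, alpha-controlled secondary test, so its dataset should be fixed before anyone sees OS by arm. As written, a statistician following 10.3.4 would analyse Part A alone, and one following 10.1 or 10.2 would add Part B participants once monotherapy DFS is positive. The cross-references do not settle the matter, because 10.3.4 has no pooling step, no pooled event count and no statement about Part B placebo participants.

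Final monotherapy DFS and final combination OS are both expected at about month 84, so the condition for pooling could be met just as the final OS look falls due. If the choice of dataset were left until then, it could decide whether OS is declared significant.

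**Working it through.** **1. Reproduce the 10.3.4 figures.** With 1:1 allocation, critical HR = exp(−2z/√d), where z is the normal quantile for the stated two-sided P and d is deaths.

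| Deaths | Stated P | Computed HR | Stated HR |
|---|---|---|---|
| 178 | 0.009 | 0.676 | 0.68 |
| 201 | 0.012 | 0.702 | 0.70 |
| 235 | 0.023 | 0.743 | 0.74 |
| 287 | 0.045 | 0.789 | 0.79 |

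Lan-DeMets O'Brien-Fleming bounds at 178/201/287 give P of 0.0089/0.0123/0.0452, as stated. A true OS HR of 0.70 gives cumulative power of 40.6%/52.7%/85.0% (stated 41/53/85). An exponential model of Part A alone, set to 287 deaths at month 84, gives about 180/205/236 deaths at months 56/62/70 (stated 178/201/235). The 10.3.4 design is therefore sound, and it is sized for Part A only.

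**2. Which looks are affected.** Combination OS looks fall at months 56, 62 or 70, and 84. Monotherapy DFS is expected at month 76 (interim) or 84 (final). Pooling can therefore reach only the month-84 look.

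**3. Pooled deaths at month 84.** The plan states no design OS HR. Take 0.70, implied by step 1, with exponential survival and equal hazards in both Parts.

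- Part A accrual over months 0–36 and 287 deaths at month 84 give a control median of 86.4 months.
- Part B accrual over months 36–56 then gives 38.3 deaths among 200 combination participants and 52.4 among 200 placebo participants.
- Total: 287 + 38.3 + 52.4 = 377.7, about 378. Part B supplies 91/378 = 24%.
- With HR varied over 0.65–0.75 and a delay in effect of 0 or 3 months, the total stays at 377.7–378.4.

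**4. Final boundary.** Alpha at the interim looks is spent on the 287-death plan, and the remainder at the final look.

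| Earlier looks | Part A only: P, HR | Pooled, both Part B arms: P, HR |
|---|---|---|
| 201 only | 0.0455, 0.790 | 0.0425, 0.812 |
| 178 and 235 | 0.0416, 0.786 | 0.0350, 0.805 |

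These are the two possible paths. An OS look at 178 deaths requires DFS to be significant at month 56, and the next look is then at 235. A look at 201 means that there was none at 178.

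**5. How often the question arises.** Inputs are the stated powers: combination DFS 90% overall and 83% at its interim; monotherapy DFS 60%; OS 53% by 201 deaths and 68% by 235. OS stopping is treated as independent of DFS.

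- Combination DFS interim held: 0.60 × [0.83 × (1 − 0.68) + 0.07 × (1 − 0.53)] = 0.179, where 0.07 = 0.90 − 0.83.
- Final DFS analysis only: 0.60 × 0.90 × (1 − 0.53) = 0.254.

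So about 18–25% of trials reach month 84 with both DFS tests positive and OS still open.

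**6. How often the answer differs.** Simulated score paths that had not crossed at an interim look were tested at 287 and at 378 deaths with the step 4 bounds. Disagreement on significance:

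| True OS HR | 201 only | 178 and 235 |
|---|---|---|
| 0.70 | 20.4% | 29.0% |
| 0.75 | 23.4% | 27.3% |
| 0.80 | 21.2% | 21.3% |

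At 0.70 the pooled test alone is significant in 18.5% / 26.3%, and the Part A test alone in 1.9% / 2.7%.

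**7. Over all trials, at HR 0.70.**

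- Final DFS only: 0.254 × 0.204 = 5.2%.
- DFS interim held: (0.60 × 0.83 × 0.32) × 0.290 + (0.60 × 0.07 × 0.47) × 0.204 = 4.6% + 0.4% = 5.0%.

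At HR 0.75–0.80, with the stated DFS powers kept, the rate is about 8–9%, because fewer trials stop early for OS.

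**The case against.** The strongest reply is that the intent is clear. The Revised Protocol 04 rationale (Document History and Appendix 8) says that OS is tested alongside DFS and in the same participants as DFS. Section 4 agrees, and 10.1 and 10.2 both defer to 10.3.4. On this view the pooling statements are leftovers in descriptive text. That is probably right, and it favours the Part A-only fix. It does not remove two current statements of a different dataset.

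Second, the separate SAP is not in the supplied text and may hold a rule. This limit stands, although an SAP rule would still leave the protocol sections in disagreement.

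Four stronger readings are tempting, and the documents do not support them.

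- *10.1 and 10.2 contradict each other.* Section 10.1 is silent on Part B placebo and does not exclude it. A combination-versus-placebo test drawn from the 10.2 population would use those two arms of both Parts.
- *Monotherapy DFS is a rival gate, so every OS look is in doubt.* Section 10.3.4 makes combination DFS the gate, and the looks at months 56, 62 and 70 precede any monotherapy DFS result.
- *Type I error is materially inflated.* An excess computed from looks at both 178 and 201 deaths uses a path that 10.3.4 rules out. After a look at 201 only, keeping P < 0.045 on 378 deaths would spend about 0.0506. The spending function is specified; the dataset it applies to is not.
- *The two datasets would often give different answers.* The 20–29% is conditional, and most of it reflects about 91 extra deaths. Amendment 05 added a final-only route for Part A DFS because the conditions for its interim had not been met, so the lower, 201-only column is the more relevant one.

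**Conclusion.** The inconsistency is real and narrow. Sections 10.1 and 10.2 conflict with 10.3.4 on who enters the combination OS test, and 10.3.4 does not contain the pooling rule to which they refer. Its 287 deaths, P < 0.045 and critical HR 0.79 are correct for Part A and would not apply to a pooled test. Primary DFS in both Parts and the interim OS looks are unaffected.

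The effect is modest: a critical HR of about 0.81 instead of 0.79 at the final look, and opposite OS conclusions in about 5% of all trials at HR 0.70. These sizes rest on an OS HR that the plan does not state (0.70–0.80 examined), equal hazards in both Parts, and independence of OS stopping from DFS. Positive correlation between the two endpoints would probably lower the overall rate. The text should be corrected because the test is confirmatory and most disagreements would favour the pooled dataset, so the choice should not be open once OS data are visible.

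**What to change.** Before OS is unblinded:

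1. Delete the sentence in 10.1 that adds Part B combination participants to combination OS, and the contingency text under the all-randomized population in 10.2.
2. State in 10.2 and 10.3.4 that confirmatory combination OS is tested in all randomized Part A participants, after Part A DFS is significant.
3. Report any pooled Part A + B comparison of the combination with placebo as descriptive, with concurrent Part B placebo participants included and stratification by Part.
4. Confirm that the separate SAP says the same.

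This costs wording only, needs no new data and keeps every figure in 10.3.4.

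If the sponsor wants a confirmatory pooled test instead, 10.3.4 must state its gate, alpha, event count and boundary, include concurrent Part B placebo and stratify by Part. That option needs a recalculated final boundary.
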